### 4.2.2 Secondary Study Endpoints

Technical effectiveness endpoint

Technical success, defined as:

- Successful data transmission of the HemoPill acute to the HemoPill Receiver.

Safety endpoints:

Adverse events / complications associated with trial or control procedure, such as:

Trial procedure:

- Aspiration of the capsule on ingestion
- Delayed excretion, or failure to excrete the capsule (capsule retention)
- Obstruction of the digestive tract
- Injury to tissue structures during the passage of the HemoPill acute through the digestive tract.

Control procedure:

- Cardiopulmonary adverse events
- Infection
- Perforation
- Bleeding (iatrogenic)

These secondary endpoints were chosen as they potentially provide meaningful information on the safety (number and type of adverse events / complications) and performance (successful data transmission) of the subject device.

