### ***5.7 Participant Withdrawal or Termination***

#### ***5.7.1 Reasons for Withdrawal or Termination***

Participants are free to withdraw from participation in the study at any time upon request. An investigator may terminate participation in the study if:

- Any clinical adverse event (AE), laboratory abnormality, or other medical condition or situation occurs such that continued participation in the study would not be in the best interest of the participant
- The participant meets an exclusion criterion (either newly developed or not previously recognized) that precludes further study participation
- Decision for conducting endoscopy is reversed for any reason

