### 10.2 Statistical Hypotheses

Formal hypotheses are only specified for the primary clinical effectiveness endpoint, the detection of blood in the gastrointestinal lumen with both measurements.

The assumed null hypothesis is that the accuracy of the HemoPill acute measurement in comparison with endoscopic finding is 50%, equaling a random distribution and no relation between these measurements. As the alternative hypothesis, it is assumed that the accuracy is equal or higher to 75%. This concrete accuracy value is derived from previous results of Brunk et al. (2021), see section 2.1.

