### 10.3 Analysis Datasets

All patients with full study protocol participation are included in the analysis dataset, i.e. with results on both measurements, the subjective device (HemoPill acute capsule) and the control product (endoscopy). Therefore, only patient withdrawal or termination by the investigator can lead to exclusion from the analysis dataset (described in detail in section 5.7).

No further (sub-)analysis datasets are planned.

---

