### 10.4.2 Analysis of the Primary Efficacy Endpoint(s)

The original continues data level of the subject device, HemoPill acute, the so-called HI-value, is transformed during the study process by the investigator in dichotomous values, negative or positive for GI lumen bleeding, i.e. negative or positive output results (described in detail in section 2.1.2.2).

The qualitative visual data of the control product, the endoscopy, is also transformed during the study process by the investigator in dichotomous values, negative or positive for GI lumen bleeding, i.e. negative or positive output results (described in section 4.1).

After the study process the values of these two factors (HemoPill acute: negative or positive, endoscopy: negative or positive) are combined in a 2 x 2 contingency table with four possible results:

- True positive: HemoPill acute measurement positive; Endoscopy measurement positive
- False positive: HemoPill acute measurement positive; Endoscopy measurement negative
- True negative: HemoPill acute measurement negative; Endoscopy measurement negative
- False negative: HemoPill acute measurement negative; Endoscopy measurement positive

(for detailed description see section 4.1)

From this 2 x 2 contingency table the summary three test indices are calculated accuracy (ACC, = (TP + TN) / pop), sensitivity (true positive rate) and specificity (true negative rate).

The significance of these results will be analyzed using the  $\chi^2$  test, goodness-of-fit test of a 2 x 2 contingency table with two tailed p-value of  $\alpha \leq .05$ .

The data assumption of the  $\chi^2$  test, goodness-of-fit test, a required minimal expected cell size of 5, will be controlled. After the inference analysis the 95% confidence intervals of the test indices can be calculated. If either of both measurement results is missing for a patient, the whole subject is omitted from the data analysis.

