#### **10.4.3 Analysis of the Secondary Endpoint(s)**

Secondary study endpoints as described in chapter 4.2.2 are technical and safety endpoints. These are solely documented, and their respective prevalence is calculated and described in relation to the total number of participants. Presentation in study reporting will either be as a percentage value (e.g., “in 2 % of patients, …”), as a number of occurrences as a fraction of total number of patients or a subgroup thereof (e.g., “in 4 of 50 patients, …”; “in 3 of the 22 patients with an endoscopically identified bleeding pathology”).

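### Accuracy is analysed only among readable capsules, one sentence of 10.3 says otherwise, and no planned analysis shows the effect on sensitivity and specificity

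*Combined protocol and SAP*

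**What the plan says.** - **10.4.2 (primary analysis).** Each patient falls into one of four cells, and the indices are computed from those cells. There is no cell for a capsule that was swallowed but gave no result. The missing-data rule is: "If either of both measurement results is missing for a patient, the whole subject is omitted from the data analysis".
- **10.3, first sentence.** The dataset is patients with full participation, "i.e. with results on both measurements, the subjective device (HemoPill acute capsule) and the control product (endoscopy". This is the same complete-case rule.
- **10.3, second sentence.** It then infers that "only patient withdrawal or termination by the investigator can lead to exclusion from the analysis dataset", pointing to 5.7. It adds that no further analysis datasets are planned.
- **5.7.1.** The investigator's reasons for termination are a medical event or situation, an exclusion criterion, and "Decision for conducting endoscopy is reversed for any reason". Capsule or transmission failure is not among them.
- **4.2.2 and 10.4.3.** Technical success is a secondary endpoint, defined as "Successful data transmission of the HemoPill acute to the HemoPill Receiver". For the secondary endpoints, "their respective prevalence is calculated and described in relation to the total number of participants".
- **2.1 (earlier multicentre series).** One of 61 patients was excluded because data transfer stopped after 10 minutes.

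**The concern.** Take a patient who swallows the capsule, loses transmission and goes on to endoscopy. The rule in 10.4.2 removes that patient; the second sentence of 10.3 gives no ground for doing so. The two statements fit together only if capsules never fail, and the plan does not assume that, since it makes transmission a secondary endpoint.

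A lost reading is an outcome of the device under test, unlike a withdrawal or a cancelled endoscopy. Removing it means that the three indices describe capsules that worked. That is a legitimate quantity, but it is at least as favourable as what a user gets from every capsule swallowed. Technical success gives the overall failure rate. It does not say whether the failures fell in patients with or without blood at endoscopy, and that decides whether sensitivity or specificity is affected. With no further datasets (10.3) and no exploratory analyses (10.4.9.2), no planned table shows it.

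The plan also does not say whether an interrupted recording is a missing result. If left open, that would be settled once the results are known.

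**Working it through.** **1. The plan's own figures.** For 50% against 75% accuracy (10.2), w = sqrt(2 × 0.25² / 0.5) = 0.50. A chi-square test with 1 df at alpha 0.05 and power 0.90 then needs N = 43 (power 0.906). Dropout: 43 / (1 − 0.14) = 50, so 7 of 50 may be lost. Both figures in 10.5 reproduce. (The printed w = 0.62 would give 28 at 1 df; that is a separate matter.) The 2% dropout precedent matches 1/61 = 1.6%, a stopped data transfer. The 7% precedent matches 2/30 = 6.7%, the pre-market trial in 2.2.5, which analysed 28 of 30.

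**2. Accuracy with failures counted as incorrect.** Assumptions: 50 enrolled, all with an endoscopy result; 75% accuracy among readable capsules; every non-evaluable patient is a capsule failure. Let f be the number of failures.

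Accuracy over all swallowed = 0.75 × (50 − f) / 50

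| f | Readable | Accuracy over 50 | Loss (points) | Chance that chi-square rejects 50% |
|---|---|---|---|---|
| 0 | 50 | 75.0% | 0 | 0.97 |
| 1 | 49 | 73.5% | 1.5 | 0.95 |
| 3 | 47 | 70.5% | 4.5 | 0.88 |
| 4 | 46 | 69.0% | 6.0 | 0.82 |
| 7 | 43 | 64.5% | 10.5 | 0.59 |

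The last column is the exact binomial probability of at least 32 correct of 50, the smallest count above 25 at which the uncorrected chi-square test rejects. For comparison, 43 complete cases at 75% (rejection at 28 or more) give 0.95.

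**3. The ceiling case, f = 7.**

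- Complete cases: 32/43 = 74.4% (95% CI 58.8 to 86.5). Chi-square = 2 × (32 − 21.5)² / 21.5 = 10.26, p = 0.001; exact binomial p = 0.002.
- All 50: 32/50 = 64.0% (95% CI 49.2 to 77.1). Chi-square = 2 × (32 − 25)² / 25 = 3.92, p = 0.048; exact binomial p = 0.065.
- One fewer correct: 31/43 = 72.1% (p = 0.004) becomes 31/50 = 62.0%, chi-square = 2 × (31 − 25)² / 25 = 2.88, p = 0.09.

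With four failures, 34/46 = 73.9% becomes 34/50 = 68.0%, chi-square = 2 × (34 − 25)² / 25 = 6.48, p = 0.011.

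**4. Why the overall failure rate is not enough.** Overall accuracy can be rebuilt under the assumptions in step 2: 74.4% × 43/50 = 64.0%. Sensitivity and specificity cannot. As an illustration, take the earlier series as the plan uses it: 20 of 60 with bleeding, sensitivity 100%, specificity 25/40 = 62.5%. With one failure in 50, 49 are readable, of whom 49 × 20/60, about 16, have blood and 33 do not.

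- Failure in a patient with blood: sensitivity 16/16 = 100% becomes 16/17 = 94.1%; specificity is unchanged.
- Failure in a patient without blood: 0.625 × 33 = 20.6 correct, and specificity 62.5% becomes 20.6/34 = 60.7%; sensitivity is unchanged.

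The same technical success rate (49/50) fits both.

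**The case against.** The strongest defence is that the complete-case rule is stated consistently in 10.4.2 and the first sentence of 10.3, so the fault is one loose inference inside 10.3. The objective in 3.1 is the relation between capsule measurement and endoscopy. Accuracy among readable results, with technical success alongside, answers it. Failures are disclosed over all participants, and 10.4.9.1 promises a listing by subject. A missing reading is also visible to the user and is not the same as a wrong one. All of this stands. It is why the complete-case table should stay primary, and why nobody should infer that failures are hidden or that the two sections disagree throughout. A listing is still not a prespecified analysis, and it leaves open what counts as missing.

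The defence also holds on size. A reader might infer from the ceiling case that counting failures would overturn the primary result. The documents do not support that. The planned test is chi-square, and 32/50 still passes it; only an exact binomial test gives p above 0.05. Nor are seven capsule failures a forecast. The 14% in 10.5 is twice the highest earlier dropout ratio and covers every kind of loss. The documented transmission failure is 1 of 61. In the pre-market trial the one failure described was a human read-out error, in a step since automated, with no device deficiencies observed, so its 2 of 30 is not a capsule failure rate.

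Finally, one might score every interrupted recording as incorrect. That would discard valid results: under Tables 3 and 4 in 2.1.3, a value at or above the positive threshold is already interpretable even if transmission stops later.

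**Conclusion.** The point holds as a cheap improvement. The second sentence of 10.3 is inconsistent with the sentence before it and with 10.4.2. The three primary indices are conditional on a readable capsule, and nothing planned shows what failures do to sensitivity and specificity.

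The likely effect on accuracy is small: about 1.5 points at 1 failure in 50, close to the documented rate. At 3 to 4 failures, roughly the 7% dropout precedent, it is 4.5 to 6 points. In the ceiling case the estimate falls from 74% to 64% and the result becomes borderline (planned chi-square p = 0.048, exact p = 0.065), which is not a reversal under the planned test. These figures assume 75% accuracy among readable capsules (32/43 in the ceiling case), that every lost patient is a capsule failure with an endoscopy result, and that a failure counts as incorrect. The true failure rate in this trial is unknown.

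**What to change.** 1. Correct the second sentence of 10.3 to match 10.4.2, so that a missing capsule or endoscopy result is named as a ground for exclusion alongside withdrawal and termination.
2. Keep the complete-case table as the primary analysis.
3. List exclusions by cause: withdrawal, termination, no endoscopy result, no capsule result.
4. Add one prespecified sensitivity analysis of all patients who swallowed a capsule and have an endoscopy result. A capsule with no interpretable result counts as incorrect. An interrupted recording that had already met the plan's own positive threshold keeps that positive result.
5. For patients with no capsule result, state in advance how blood below 20 mL at endoscopy is classed. The quantity condition in 4.1 applies only when the capsule is negative, so without a rule such a patient could fall under either sensitivity or specificity.

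The cost is one extra table and possibly a slightly less favourable figure. Sample size and procedures do not change, and if every capsule gives a result the added table equals the primary one.

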#### **10.4.3 Analysis of the Secondary Endpoint(s)**

Secondary study endpoints as described in chapter 4.2.2 are technical and safety endpoints. These are solely documented, and their respective prevalence is calculated and described in relation to the total number of participants. Presentation in study reporting will either be as a percentage value (e.g., “in 2 % of patients, …”), as a number of occurrences as a fraction of total number of patients or a subgroup thereof (e.g., “in 4 of 50 patients, …”; “in 3 of the 22 patients with an endoscopically identified bleeding pathology”).

#### **10.4.4 Safety Analyses**

Among the secondary endpoints, safety endpoints are defined (see chapter 4.2.2). Occurrences are documented, and their respective prevalence is calculated and described in relation to the total number of participants. Safety oversight measures are described in chapter 8.7. The Study will be halted after two SAEs (see chapter 8.4.2).

#### **10.4.5 Adherence and Retention Analyses**

The successful consumption of the subjective device, the HemoPill acute capsule, is controlled by the administering investigator (see section 6.3.1). No further adherence analyses are planned. Retention analyses are not applicable in this study design.

#### **10.4.6 Baseline Descriptive Statistics**

Baseline demographic, clinical and procedural data will be summarized using descriptive statistics. For continuous variables (such as age), results will be summarized with the numbers of observations, minimums, maximums, means, and standard deviations and where specified in table or figure conventions with quartiles.

For categorical variables (such as gender) results will be summarized with subject counts and percentages. Inferential statistics are not planned for the baseline statistics, because no subgroups are compared within the sample, nor comparisons with epidemiological or demographic data are planned.

#### **10.4.7 Planned Interim Analysis**

Not applicable.

#### **10.4.8 Additional Sub-Group Analyses**

No analyses of based on age, sex, race/ethnicity or other demographic characteristics are planned.

#### **10.4.9 Multiple Comparison/Multiplicity**

Not applicable.

##### **10.4.9.1 Tabulation of Individual Response Data**

The individual participant data will be listed by subject with measurement result and time point for each subject.

##### **10.4.9.2 Exploratory Analyses**

No exploratory analyses are planned.

## 10.5 Sample Size

The study will enroll in total n = 50 participants:

- at least 43 eligible for statistical analyses
- plus 7 as highest expectable dropout count.

The required sample size of n = 43 was calculated for the planned  $\chi^2$  test for the test indices (accuracy, sensitivity and specificity). The calculation was based on the previous clinical study of Burk et al. (2021) which provide an accuracy of 75% (sensitivity of 100% and specificity of 63%) equaling an assumed effect size  $w = 0.62$ . The calculation was done with an a priori set  $\alpha$  error of .05 and a targeted power (1- $\beta$ ) equal or higher than .90.

Based on the previous studies dropout ratios between 2% (Burk et al., 2021) and 7% (Caca & Zimmermann, 2017) could be expected. By reason of clinical judgement, a maximal dropout ratio of 14% was assumed (which equals two times the maximal previous dropout ratio). An assumed maximal dropout of 14% equals 7 additional participants (when targeting at least 43 participants eligible for statistical analyses).

The targeted n = 43 also assures the required minimal expected cell size of 5 for a  $\chi^2$  test being applicable. The method of power analysis was an a priori required sample size computation with given  $\alpha$ , power and effect size. The power analysis was conducted with the computer program G\*Power 3.1 (Faul et al., 2009).

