## 10 Statistical Considerations

### 10.1 Statistical and Analytical Plans (SAP)

No additional formal SAP is provided.

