## 10.4 Description of Statistical Methods

### 10.4.1 General Approach

This study has a double blinded, prospective diagnostic case-control design. This prototypic design of diagnostic accuracy study is a consecutive series of individuals in whom the target condition is suspected, here GI lumen bleeding. The index test, here HemoPill acute, is performed first in all participants. Subsequently, the presence of the target condition is also measured in all participants with the reference standard, in this case endoscopy (Rutjes et al. 2005).

In more detail, this study is performed:

- on one sample: the study is conducted on a single sample (single-arm) at a single center
- double blinded: neither the patients nor the investigators are aware of the result of the subjective device, the HemoPill acute capsule, during the examination of the control product, the endoscopy.
- with repeated measurement: all patients are measured with the subjective device and additionally with the control product
- case-control design: the status of a patient with positive endoscopy result equals as classification in the case group, the status of a patient with negative endoscopy result equals as classification in the control group. This classification is determined after the study process, during the statistical analysis to ensure double blindness.

The categorical variables (such as positive or negative test results) will be summarized with subject counts, respectively frequency, and percentages.

As inferential test a  $\chi^2$  test, goodness-of-fit test of a 2 x 2 contingency table with two tailed p-value of  $\alpha \leq .05$  will be used.

The assumption of the  $\chi^2$  test, goodness-of-fit test, a required minimal expected cell size of 5, will be controlled (and is a priori controlled in the power analysis, see section 10.5). The dichotomous data level of the two factors, results of subjective device and results of control product, are transformed into a cell count, observed cases, in the 2 x 2 contingency table.

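### The effect size in section 10.5 (w = 0.62) fits neither n = 43 nor the accuracy hypothesis in 10.2 (w = 0.50, which gives 43), and the 90% power claim has no basis for sensitivity or specificity

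*Combined protocol and SAP*

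**What the plan says.** Section 10.2 restricts formal testing: "Formal hypotheses are only specified for the primary clinical effectiveness endpoint". It then gives one null, "The assumed null hypothesis is that the accuracy of the HemoPill acute measurement in comparison with endoscopic finding is 50" per cent, and an alternative of 75% or more. No null value is given for sensitivity or specificity.

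Section 10.5 states that "The required sample size of n = 43 was calculated for the planned" chi-square "test for the test indices (accuracy, sensitivity and specificity"), using a prior study "which provide an accuracy of 75% (sensitivity of 100% and specificity of 63%) equaling an assumed effect size" of w = 0.62, alpha .05, power of at least .90, and G*Power. It gives no degrees of freedom.

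Section 10.4.1 names the test as a chi-square "goodness-of-fit test of a 2 x 2 contingency table with two tailed p-value of" .05 or less. Section 10.4.2 derives accuracy, sensitivity and specificity from the table and continues: "The significance of these results will be analyzed using the" same test. Neither section gives the null cell proportions or the degrees of freedom, and section 10.1 says: "No additional formal SAP is provided".

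**The concern.** Section 10.5 presents 75% accuracy and w = 0.62 as the same quantity. Against the 50% null in 10.2 they are not, and w = 0.62 does not lead to 43 in a 2 x 2 table. A reader who repeats the calculation from the stated effect size gets a smaller number and cannot tell which test was powered or which will be run.

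The second issue is interpretation. Specificity is the weaker index in the planning data (63%). If the report repeats that 43 patients gave 90% power for all three indices, an imprecise specificity may be read as the outcome of a well-powered comparison, although the plan defines no such comparison.

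**Working it through.** **Inputs.** Null accuracy 50% and alternative 75% (10.2). Alpha .05 two-sided (10.4.1, 10.5), power at least .90, w = 0.62, sensitivity 100%, specificity 63% (10.5). Prior 12-hospital series (background literature, 2.1): 60 patients, 35 capsule-positive, of whom 20 had bleeding seen at endoscopy, and 25 capsule-negative with no proven bleeding. Hence TP 20, FP 15, FN 0, TN 25. These cells give accuracy 45/60 = 75%, sensitivity 20/20 = 100% and specificity 25/40 = 62.5%, which are the planning values in 10.5.

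**Method.** w = sqrt(sum of (p1 - p0)^2 / p0). Power is the probability that a noncentral chi-square with the given df and noncentrality n x w^2 exceeds the 5% critical value.

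**1. Reproducing n = 43 from 10.2.** Correct against incorrect, 0.75/0.25 v 0.50/0.50:
w = sqrt(0.25^2/0.50 + 0.25^2/0.50) = sqrt(0.25) = 0.50.
At 1 df, power is 0.8998 at n = 42 and 0.906 at n = 43. The smallest n reaching .90 is therefore 43, the plan's figure. Dropout is consistent too: 43/(1 - 0.14) = 50.

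**2. Where 0.62 may come from.** The four prior-series cells against 25% each:
- TP: (0.333 - 0.25)^2/0.25 = 0.0278
- FP: (0.25 - 0.25)^2/0.25 = 0
- FN: (0 - 0.25)^2/0.25 = 0.25
- TN: (0.417 - 0.25)^2/0.25 = 0.1111

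The sum is 0.3889, so w = 0.624. A test of independence on the same table has w = 0.598.

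**3. n required for power .90 at each effect size.**

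| Effect size | df | n needed | Power at n = 43 |
|---|---|---|---|
| 0.50 (accuracy 75% v 50%) | 1 | 43 | 0.906 |
| 0.62 | 1 | 28 | 0.98 |
| 0.62 | 3 | 37 | 0.94 |
| 0.598 (independence) | 1 | 30 | not needed here |

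With w = 0.62, n = 43 appears only at 5 df, which a 2 x 2 table does not have.

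**4. Equal cells is not the 10.2 null.** Suppose all 43 capsules read positive and 21 are correct. Accuracy is 21/43 = 49%. Against 10.75 expected per cell, chi-square = (21 - 10.75)^2/10.75 + (22 - 10.75)^2/10.75 + 10.75 + 10.75 = 9.77 + 11.77 + 21.5 = 43.0, far above the 3-df critical value of 7.81. A fit to equal cells can therefore be strongly significant when accuracy is about 50%.

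**5. Specificity, illustration only.** The 50% null is an assumption; the documents give none. The number of endoscopy-negative patients is also assumed. The prior split gives 43 x 40/60 = 28.7. Leaving out the prior-series patients without endoscopy (4 capsule-positive without EGD, 5 capsule-negative) gives 43 x 31/51 = 26.1. For 63% v 50%, w = 0.13/0.50 = 0.26.

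| Endoscopy-negative | Exact binomial | Noncentral chi-square |
|---|---|---|
| 26 | 0.196 | 0.263 |
| 27 | 0.161 | 0.272 |
| 28 | 0.236 | 0.280 |
| 29 | 0.197 | 0.288 |
| 43 (upper limit) | 0.332 | 0.399 |

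Under the same assumed null, sensitivity at 100% shows no shortfall: with 14 or 15 endoscopy-positive patients, power is 0.96 or more. As to precision, 18/29 correct negatives would have an exact 95% interval of 42-79%.

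**The case against.** The strongest reply is that the sample size is right and only one number beside it is wrong. The null, alternative, alpha, power and software are all in the documents, and together they return 43 exactly. That stands. A reader might infer from the mismatch that n = 43 has no derivation or cannot be checked; the documents do not support this, since 10.2 and 10.5 together yield it at 1 df. A reader might also infer that the trial is underpowered. It is not: power for the formal hypothesis is 0.906, and the stated w = 0.62 would make it higher.

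A second reply is that 10.5 refers to one test on one table, so the three indices in parentheses need not be three separate power claims. That is a fair reading, and it is why the 16-29% is not a measured shortfall of a planned test: both the null and the case split behind it are assumed. But the wording does attach the calculation to sensitivity and specificity by name, and 10.4.2 attaches significance testing to all three indices, so the text needs limiting.

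A third reply is that correcting w and stating the df would be enough, without renaming the test. This stands in part. An exact binomial is a preference and not a necessity. Naming a one-sample accuracy test is not mere preference, because a goodness-of-fit test of the table with unstated null proportions may be taken as a fit to equal cells, which does not test the 10.2 hypothesis.

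**Conclusion.** The concern holds in a limited form. The stated w = 0.62 is inconsistent with n = 43 (28 or 37 would follow) and with the accuracy hypothesis (w = 0.50). Its match to the prior-series cells against 25% each (0.624) is an inference; the documents do not say how 0.62 or 43 was obtained. For accuracy, n = 43 meets the .90 target on every reading considered: 0.906, 0.94 or 0.98.

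The power claim for sensitivity and specificity lacks a basis because no null is stated for either. The size of the gap for specificity (about 16-29%, and 33-40% even if all 43 patients were endoscopy-negative) depends on an assumed 50% null and should be cited only as illustration. This should be corrected in the text; it does not threaten the primary comparison.

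**What to change.** - **10.5:** replace w = 0.62 with w = 0.50, 1 df: a one-sample test of accuracy, 75% v 50%, two-sided alpha .05, power 0.906 at n = 43. Present this as the justification now relied on, since the documents do not show the route originally used. Limit the 90% power statement to accuracy.
- **10.4.1 and 10.4.2:** name that one-sample accuracy test as the primary test, in place of the 2 x 2 goodness-of-fit test.
- **Sensitivity and specificity:** report as estimates with exact 95% confidence intervals, without a power claim.
- **Optional:** use the exact binomial and say so in all three sections. It rejects in favour of the device at 29 or more correct of 43, with two-sided size 0.032 and power 0.904. The uncorrected 1-df chi-square rejects from 28 of 43 (p = 0.047), where its true two-sided size is 0.066. Because the boundary differs by one patient, the choice should be fixed before accuracy results are seen.

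The cost is text in three sections. The 43 evaluable patients and the enrolment of 50 do not change. The plan gives up its stated 90% power for sensitivity and specificity.

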Only n=1 serious adverse event occurred during the study which, according to physicians, had no causal relationship to the use of the investigational device. Capsule ingestion was well tolerated in all patients. Passage and excretion of the HemoPill acute was observed without any adverse events or complaints by the patients. Furthermore, no adverse device effects or device deficiencies could be observed during the trial, thus the sensor capsule and the study receiver can be considered as safe devices that performed as expected in all n=30 subjects.

n=1 human failure occurred during the read-out procedure of the sensor capsule data from the study receiver and was due to the wrong order in manual program execution. This failure is not relevant for the final receiver device because the read-out procedure was automated for the final device.

Sensitivity and specificity assessment of the HemoPill acute in detecting the presence of blood in the upper GI tract proved to be favorable in patients with  $> 20$  ml of blood: sensitivity = 100 % (95 % confidence interval (CI), 54 to 100 %) and specificity = 83 % (95 % CI, 60 to 95 %). However, comparatively wide 95 % confidence intervals must be considered due to the low subject number included in the analysis.

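### If the chi-square test is one of association, n = 43 does not guarantee expected cells of at least 5, and no test is named for when they fall short

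*Combined protocol and SAP*

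**What the plan says.** Section 10.5 plans for "at least 43 eligible for statistical analyses" and adds: "The targeted n = 43 also assures the required minimal expected cell size of 5 for a" chi-square test. Sections 10.4.1 and 10.4.2 describe the test as a "goodness-of-fit test of a 2 x 2 contingency table with two tailed p-value of" 0.05 or less. Section 10.4.2 says of the test's assumption: "a required minimal expected cell size of 5, will be controlled". Section 10.4.1 says that the power analysis has already dealt with it.

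Section 10.2 gives the null as 50% accuracy and equates this with a random distribution and with the two results being unrelated. For planning, the prior series is said to "provide an accuracy of 75% (sensitivity of 100% and specificity of 63%) equaling an assumed effect size" w of 0.62, with an alpha "error of .05 and a targeted power" that is "equal or higher than .90".

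The plan states no degrees of freedom, expected counts or share of endoscopy-positive patients. It names no test to use if the cell condition fails, and section 10.1 says there is no separate SAP.

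**The concern.** For a test of whether two binary results are related, each expected count is row total times column total divided by n. It therefore depends on how many patients are endoscopy-positive and how many are capsule-positive, and the plan fixes neither. A statement that 43 patients secure the condition claims something the design does not have.

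This matters because the plan makes its only inferential test conditional on the check. If the check fails, the analyst must choose another test after seeing the table.

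**Working it through.** **Inputs.** The prior series (section 2.1) had 35 capsule-positive and 25 capsule-negative patients of 60, with bleeding confirmed in 20 of the 35. Counting every other patient as endoscopy-negative gives TP/FP/FN/TN = 20/15/0/25. This matches the planning figures: specificity 25/40 = 62.5% and accuracy 45/60 = 75%. Only 11 of the 15 and 20 of the 25 were endoscoped, so the verified table is 20/11/0/20 of 51.

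The pre-market study (section 2.2.5) analysed 28 patients and reports "sensitivity = 100 % (95 % confidence interval (CI), 54 to 100" %), with specificity 83% (60 to 95%), for more than 20 mL of blood. No counts are printed. The exact lower limit for 6/6 is 0.025^(1/6) = 0.541. An 18/22 specificity gives exact limits of 60% and 95%, and 6 + 22 = 28. The rebuilt table is 6/4/0/18.

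**The plan's own figures.**
- Effect size against four equal cells: w² = [(0.333 − 0.25)² + (0.25 − 0.25)² + (0 − 0.25)² + (0.417 − 0.25)²]/0.25 = 0.389, so w = 0.624. Against independence, phi = (20×25 − 15×0)/√(35×25×20×40) = 0.598. The stated 0.62 is therefore the equal-cell value.
- Sample size at alpha 0.05 and power 0.90 (noncentral chi-square, noncentrality n·w²): w = 0.62 needs 28 with df 1, 37 with df 3, and 43 only with df 5, which no 2 x 2 table has. Accuracy of 50% against 75% (w = 0.50, df 1) gives 43, with power 0.906.

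**Smallest expected cell at n = 43, test of association (average margins).**
- Prior series: 43 × (20/60) × (25/60) = 5.97
- Endoscoped patients only: 43 × (20/51) × (20/51) = 6.61
- Rebuilt pre-market rates: 43 × (6/28) × (10/28) = 3.29

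The room for variation is small. With 18 of 43 capsule-negative, 12 endoscopy-positives give 12 × 18/43 = 5.02, and 11 give 4.60.

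**Probability that the smallest expected cell is below 5** (all possible tables enumerated, multinomial weights):

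| True rates | n = 43 | n = 50 |
|---|---|---|
| Prior series, 60 patients | 25.4% | 7.0% |
| Prior series, 51 endoscoped | 10.7% | 1.8% |
| Rebuilt pre-market rates | 84.3% | 75.5% |

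Holding sensitivity at 100% and specificity at 62.5%, simulation at n = 43 gives 85% when 20% are endoscopy-positive, 62% at 25%, 26% at 33%, 13% at 40%, 25% at 50% and 89% at 67%.

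**Readings with fixed expected counts.**
- Four equal cells: 43/4 = 10.75 each, so the condition always holds. But if capsule and endoscopy are unrelated, this test (df 3) rejects in about 52% of simulated trials at the prior-series margins and 97% at the rebuilt pre-market margins, only because the margins are not 50:50.
- Correct versus incorrect against 50%: 43/2 = 21.5 each, so again the condition always holds. This is a two-category test, not a test of a four-cell table.
- Sensitivity against 50% (section 10.5 lists sensitivity among the tested indices): expected counts are half the endoscopy-positives, so at least 10 are needed. The binomial probability of fewer than 10 of 43 is 5.5% at 20/60 and 56% at 6/28.

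**The case against.** The strongest reply is that the plan calls the test goodness-of-fit and that its w of 0.62 comes from equal cells. On that reading every expected count is 10.75 and the sentence is correct. That stands as arithmetic, and it is why the point is conditional on a test of association. It does not rescue the plan. Section 10.2 also sets a null of no relation, and section 10.4 describes a contingency table of two factors. With fixed counts the planned check would have nothing to check, and the equal-cell test answers a question about prevalence as well as agreement.

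A second reply is that little depends on the choice of test. This is largely right. Over all 43-patient tables, uncorrected Pearson and Fisher tests differ at 0.05 in 0.03% of trials at the prior-series rates, 0.003% at the endoscoped-only rates and 0.10% at the rebuilt pre-market rates. Power exceeds 99.8% throughout. Simulated Pearson type I error under independence was 5.1% at both the prior-series and pre-market margins.

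Some stronger readings are tempting but not supported:
- A reader might infer that repeating the prior series would break the condition. An exact repeat gives 5.97 and passes; the 25% is sampling variation around those rates.
- A reader might take 84% as a forecast. That table is rebuilt from confidence limits, and its 18/22 is 82%, not the printed 83%. It also uses a reference of more than 20 mL, whereas section 4.1 counts any fresh blood or hematin when the capsule is positive, which could raise the share of positives.
- A reader might say the plan ignores the possibility of failure. It does plan a check; what is missing is what follows if the check fails.

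**Conclusion.** The concern holds in conditional form. If the chi-square is a test of association, 43 evaluable patients do not guarantee expected cells of at least 5. The chance of falling short is about 25% at the 60-patient prior-series rates and 11% at the endoscoped-only rates, which are closer to this trial's both-results analysis set. It is 7% and 2% if all 50 are evaluable, and about 84% in the rebuilt pre-market scenario. These figures assume that the quoted rates are the true ones and that the expected counts come from the observed margins.

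The assurance is true only when expected counts are fixed beforehand, and the four-equal-cell version does not test the section 10.2 hypothesis. The likely effect on the association verdict is small. The defect is an unsupported statement and an unnamed fallback for the only inferential test, not a threat to the trial's conclusion.

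**What to change.** Delete the assurance sentence in section 10.5 and the minimum-cell condition in sections 10.4.1 and 10.4.2. Name the exact two-sided binomial test of accuracy against 50% as the primary test. If association is also to be tested, name Fisher's exact test. Use both whatever the cell counts.

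The two tests are not interchangeable. At the prior-series margins, unrelated results would agree in (35/60)(20/60) + (25/60)(40/60) = 47% of patients, not 50%. The text should say which null each test addresses.

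The cost is wording, plus the slight conservatism of exact tests. For accuracy, 29 or more correct of 43 is needed (two-sided level 2 × 0.0158 = 0.032; 28 would give 2 × 0.0330 = 0.066). Power at 75% accuracy is then 0.904, so the planned n = 43 still meets its 0.90 target.
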